	Evaluate the overall safety of deferasirox FCT formulation in patients with lower risk MDS at the beginning of their transfusional history	Overall safety, as measured by frequency and severity of reported AEs and SAEs and changes in laboratory values from baseline: serum creatinine, creatinine clearance ALT, AST, complete blood count (platelets, RBC and WBC) and total direct and indirect bilirubin).
	Leukemic transformation (including progression to leukemia or higher rIPSS scores)	Proportion of patients with a disease progression (progression defined as a transition into a higher MDS risk group based on revised IPSS scoring or progression to AML) Time to progression (defined as above) or to leukemia transformation.
	Hemopoietic response	Percentage of patients with hematologic improvements in term of erythroid response following IWG 2006 criteria. Time to reach transfusion dependence defined as > 2 PRBC units/months for 3 months for patients with pre-transfusional Hb < 9.0 g/dl (or <10 g/dl for patients with cardiac disease) or a total number of PRBC units received = 20 from baseline. Absolute reticulocytes count from baseline to every visit during the whole treatment period. Absolute values and evolution of serum transferrin receptor, GDF11, GDF15 and erythroferrone from baseline to every visit during the whole treatment period. Evaluation of transfusional ratio: number of units received in a

		
predetermined period/ mean pre-transfusional Hb level. Compared with other studies on general population (study and FISiM registry).
 
Patients receiving concurrent rHuEpo and other disease modifying agents will not be considered for hemopoietic response.

	Costs analysis	Cost and outcome with low dose in early chelation vs. chelation treatment in MDS patients with transfusional iron overload in accordance with either local or international guidelines
Exploratory	Study of biological cellular damage by iron toxicity before and during treatment	MDA values during the study and relationship to NTBI and LPI values

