11. STUDY DESIGN

11.1. Overview of study design

[figure not shown]
This is an open label, single arm, phase II, study.

The study includes a screening period (in which patients eligibility will be assessed) followed by a 1-year treatment period during which monthly visits will take place to evaluate safety and efficacy parameters (total 16 visits + 1 screening visit).

Study treatment with low dose (3.5 mg/kg/day) DFX-FCT will be given to all enrolled patients at the beginning of their transfusional history

Dose activity will be monitored by regular NTBI /LPI suppression and by prevention of iron accumulation as demonstrated by hepatic iron concentration, comparing baseline versus end of study iron concentration. It has been clearly demonstrated that liver iron concentration is proportional to total body iron stores (LIC x 10.6 = total body iron store in mg/kg)(39)

A standard pre-transfusional Hemoglobin level will be indicated (Hb threshold for transfusion Hb 9 g/dl or 10 g/dl for patients with cardiac disease) to be maintained during the study year. Pre transfusional hemoglobin level and transfusions date and frequencies will be recorded. A transfusional ratio will be determined: number of units received in a predetermined period/ mean pre-transfusional Hb level

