14.4.5. Contraception

Non-sterilized female patients of reproductive age group and male patients should use effective methods of contraception through defined periods during and after study treatment as specified below.

Female patients must meet 1 of the following:

- Postmenopausal for at least 1 year before the screening visit, or surgically sterile, or
- If they are of childbearing potential, agree to practice 2 effective methods of contraception from the time of signing of the informed consent form through 6 months after the last dose of study drug (since Deferasirox can reduce the effectiveness of hormonal contraceptives, it is recommended that women of childbearing age use additional or alternative non-hormonal contraceptive methods), or
- Agree to practice true abstinence, when this is in line with the preferred and usual lifestyle of the subject. (Periodic abstinence [e.g., calendar, ovulation, symptothermal, post ovulation methods] and withdrawal are not acceptable methods of contraception.)

14.5. Excluded/admitted concomitant medication.

Admitted concomitant medication: as per clinical practice. Concomitant rHuEpo is admitted and registered (patients who receive rHuEpo during the year study will not be evaluated for erythroid response). No additional experimental therapy is admitted.

A standard pre-transfusion Hemoglobin level will be indicated (Hb threshold for transfusion Hb 9 g/dl or 10 g/dl for patients with cardiac disease) to be maintained during the study year. Pre transfusion hemoglobin level and transfusions date and frequencies will be recorded.

A transfusional ratio will be determined: number of units received in a predetermined period/ mean pre-transfusion Hb level.

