	Hemopoietic response	Percentage of patients with hematologic improvements in term of erythroid response following IWG 2006 criteria. Time to reach transfusion dependence defined as > 2 PRBC units/months for 3 months for patients with pre-transfusional Hb < 9.0 g/dl (or <10 g/dl for patients with cardiac disease) or a total number of PRBC units received = 20 from baseline. Absolute reticulocytes count from baseline to every visit during the whole treatment period. Absolute values and evolution of serum transferrin receptor, GDF11, GDF 15 and erythroferrone from baseline to every visit during the whole treatment period. Evaluation of transfusional ratio: number of units received in a

		predetermined period/ Mean pre-transfusional Hb level. Compared with other studies on general population (study and FISIM-ETS registry). Patients receiving concurrent rHuEpo will not be considered for erythroid response
	Costs analysis	Cost and outcome with low dose in early chelation vs. chelation treatment in MDS patients with transfusional iron overload in accordance with either local or international guidelines
Exploratory objective and endpoint	Study of biological cellular damage by iron toxicity before and during treatment	MDA values during the study and relationship to NTBI and LPI values

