Demographic and other baseline data (including disease characteristics and transfusion history, etc) will be summarized descriptively for the Safety analysis set by means of the statistics above mentioned. Summary tables will be provided about medical history coded by System Organ Class and Preferred Term of MedDRA dictionary.

Treatments (study treatment, concomitant therapies, compliance)

The descriptive analysis listed below will be reported for the safety analysis set.

Study drug

The duration of study drug exposure, as well as average prescribed doses, will be summarized. Any dose adjustments and reasons that led to the adjustments will be listed. The number and duration of dose interruptions will also be described.

Compliance

Compliance based on prescribed amount of study medication versus amount of medication taken based on dispensed and returned amount of study medication will be summarized.

Concomitant Therapies

Concomitant medications and significant non-drug therapies prior to and after the start of the study treatment will be coded by WHO Drug Reference List dictionary and frequencies will be calculated according to drug classes.

The primary objective is prevention of iron accumulation measured by (primary variable) Change of hepatic iron from baseline according to baseline hepatic iron level: Baseline versus end of study.

For patients with baseline LIC ≤ 5 mg/g dry weight (dw) ± 1.5 mg/g dw.

For patients with baseline LIC > 5 mg/g dw $\pm 20\%$ (by R2- MRI ; test performed in a 1.5 tesla MRI machine and analyzed following R2 method (75).

The corresponding secondary efficacy variable will be the absolute change in hepatic iron concentration EOS versus baseline.

Difference between baseline versus EOT will be measured as continuous variables and analyzed with parametric or non parametric statistical tests depending by normality of distribution.

Secondary endpoint:

Observational: demographics and other baseline characteristics will be study with descriptive statistics. Analysis will be done on FAS and PP.

As the same way secondary endpoints will be evaluated as continuous or nominal variables and analyzed accordingly with parametric or non parametric tests. Efficacy parameters analysis will be done on FAS and PP.

Final Safety parameters will be measured in full analyses set and in all patients who received at least one dose of study drug (safety set).

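### The synopsis and sections 14.5 and 17.2.2 give conflicting rules on which patients are evaluable for hemopoietic response, and section 20.3 does not settle which applies

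*Combined protocol and SAP*

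**What the plan says.** Three current passages say who is left out of the hemopoietic analysis.

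- Synopsis, hemopoietic response: "Patients receiving concurrent rHuEpo and other disease modifying agents will not be considered for hemopoietic response".
- Section 14.5 (excluded/admitted concomitant medication): "patients who receive rHuEpo during the year study will not be evaluated for erythroid response".
- Section 17.2.2, hemopoietic response: "Patients receiving concurrent rHuEpo will not be considered for erythroid response".

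The objective opens with "Percentage of patients with hematologic improvements in term of erythroid response following IWG 2006 criteria". It also lists time to transfusion dependence, reticulocyte count, serum transferrin receptor, GDF11, GDF15, erythroferrone and the transfusional ratio, which is to be compared with other studies and the registry.

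On background treatment, section 14.5 says "Admitted concomitant medication: as per clinical practice" and then "No additional experimental therapy is admitted". On design, section 11.1 says "This is an open label, single arm, phase II, study". On analysis, section 20.3 says "Efficacy parameters analysis will be done on FAS and PP", with the full analysis set defined as every enrolled patient. It does not mention concomitant disease-modifying treatment.

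**The concern.** The rules differ in drug class (rHuEpo alone, or rHuEpo and other disease-modifying agents) and in scope (erythroid response alone, or the whole hemopoietic objective). Two statisticians working from the same protocol could report different numerators and denominators for the same endpoint, and each could cite the text in support.

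The choice matters because there is no concurrent control. If the body text is followed, a patient whose anaemia improves on another active agent is counted as an erythroid responder on deferasirox. Patients on rHuEpo or another agent also stay in time to transfusion dependence, the marker series and the transfusional ratio. Fewer transfusions because of a background drug would then look like an effect of chelation, including in the planned external comparison of the ratio.

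**Working it through.** The plan states no figure on this point, so there is nothing to reproduce. The check compares the texts and then gives an illustration on assumed inputs.

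**Step 1. The rules side by side.**

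| Place | Drugs that trigger the rule | Endpoints covered | Exposure |
|---|---|---|---|
| Synopsis | rHuEpo and other disease-modifying agents | Hemopoietic response | Concurrent, undefined |
| 14.5 | rHuEpo | Erythroid response | Any receipt in the study year |
| 17.2.2 | rHuEpo | Erythroid response | Concurrent, undefined |
| 20.3 | None stated | None stated | None stated |

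The synopsis phrase could be read as requiring rHuEpo and another agent together. The natural reading is either one. On both readings it differs from 14.5 and 17.2.2.

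**Step 2. Can exposure occur?** Section 14.5 follows clinical practice and bars experimental therapy only. The exclusion criteria in section 12.2 rule out recent investigational drugs and participation in other interventional trials, not licensed MDS treatment. Section 15.1 lists taking prohibited medication as a reason to stop, but no list names these agents. The synopsis rule also presupposes that such use can happen.

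**Step 3. Difference between the rules for erythroid response.** Both rules set rHuEpo users aside for this endpoint, so consider the remaining patients. Let

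- q = share on another disease-modifying agent, assumed 10-20%;
- r1 = response rate among those users, assumed 30-50%;
- r0 = response rate on deferasirox without such an agent, assumed 5-20%.

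None of these values comes from the documents.

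Body rule (users kept): rate = (1 - q) × r0 + q × r1.
Synopsis rule (users removed from numerator and denominator): rate = r0.
Difference = q × (r1 - r0).

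| r0 (synopsis rule) | q = 10%, r1 = 30% | q = 10%, r1 = 50% | q = 20%, r1 = 30% | q = 20%, r1 = 50% |
|---|---|---|---|---|
| 5% | 7.5% (+2.5) | 9.5% (+4.5) | 10% (+5) | 14% (+9) |
| 10% | 12% (+2) | 14% (+4) | 14% (+4) | 18% (+8) |
| 20% | 21% (+1) | 23% (+3) | 22% (+2) | 26% (+6) |

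Smallest: 0.10 × (0.30 - 0.20) = 0.01. Largest: 0.20 × (0.50 - 0.05) = 0.09. The range is 1 to 9 percentage points.

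**Step 4. Effect on the denominator.** Of 50 patients, removing 10% or 20% leaves 50 × 0.90 = 45 or 50 × 0.80 = 40 evaluable, before rHuEpo users are also removed.

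**The case against.** The strongest reply is that the synopsis already contains the protection. Misattribution arises only if 17.2.2 is treated as operative and the synopsis is ignored, and the documents do not say which text governs. That stands: the harm is conditional, and the certain defect is the conflict itself.

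Second, a reader might infer that the protocol expressly permits disease-modifying agents. It does not. No passage names them as allowed; they are simply not barred. How many patients will receive one is unknown.

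Third, a reader might size the problem as q × r1, which is 0.10 × 0.30 = 3% to 0.20 × 0.50 = 10%. That is the gross contribution of these patients. The synopsis rule takes them out of the denominator too, so the difference between the rules equals the gross figure only if r0 is zero.

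Fourth, hemopoietic response is one of several secondary objectives. No sample size, threshold or decision rule depends on it. The background in section 8.2 reports improved hemopoiesis under chelation in other work, but it does not make this endpoint the trial's test of benefit. Concomitant medication is also recorded and coded, so users can be identified and shown separately even without a control arm. All of this limits the weight of the point, but none of it reconciles the passages.

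Finally, keeping every patient in the descriptive marker series is a legitimate choice. It needs to be stated, and at present the synopsis and 17.2.2 point in opposite directions.

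**Conclusion.** The point holds as a conflict between current passages that section 20.3 leaves open. Following 17.2.2 as written would credit another agent's erythroid effect to deferasirox in a trial with no control. Relative to the synopsis rule, the erythroid response rate would be about 1-9 percentage points higher on the assumed inputs. The direction depends on users of other agents responding more often than the rest (r1 above r0), and the size on a usage rate that the documents do not give.

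A reader might go further and conclude that the trial's main result is compromised. The documents do not support that: neither rule applies to the liver iron endpoint, and only the hemopoietic secondary objective is affected. The correction is worth making before analysis because it is specific and cheap, and the sponsor has already recognised the confounder in the synopsis.

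**What to change.** Reconcile the synopsis, 14.5 and 17.2.2 into one analysis rule and carry it into 20.3. The rule should:

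- apply to rHuEpo and all other disease-modifying agents, with the classes named;
- cover erythroid response at least, and say for each other hemopoietic endpoint whether it applies;
- define the exposure window, including use at baseline and starts during the year;
- provide for users of these agents to be reported separately.

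This is a rule about analysis and changes no treatment. The data are already planned: section 16.6 records concomitant medication from screening to 30 days after the last dose, and section 20.3 codes it.

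Two sensitivity analyses could be offered. One keeps patients who start an agent before responding in the denominator as non-responders. This guards against the selection that arises when patients are dropped because of something that happened after baseline. The other ends follow-up at the start date of the agent. An agent may be started because anaemia is worsening, so this censoring may be informative and could itself lengthen the apparent time to transfusion dependence. Neither approach appears in the current texts, and statisticians may differ on them, so they should not replace the main rule by default.

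The cost is protocol and SAP wording, fewer evaluable patients, and possibly a slightly lower reported response rate.

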18. SAFETY MONITORING AND REPORTING

Safety monitoring will be based on the i) evaluation of changes from baseline throughout the whole study in physical examination, heart rate/rhythm, blood pressure, renal function, liver function and laboratory findings, ii) a global assessment of organ function; and iii) the observation and report of any adverse event (AE).

18.1. Adverse Events

An adverse event is defined as the appearance of (or worsening of any pre-existing) undesirable sign(s), symptom(s), or medical condition(s) that occur after patient's signed informed consent has been obtained.

Once the study ICF is signed, all AEs will be captured in the Adverse Event CRF.

The severity of an AE will be assessed on the basis of the NCI CTCAE version 4.03 (please see forreference:https://evs.nci.nih.gov/ftp1/CTCAE/CTCAE_4.03_2010-06-14_QuickReference_8.5x11.pdf.).

All non-Serious Adverse Events, all reports of drug exposure during pregnancy, all reports of misuse and abuse of the drug, all reports describing the occurrence of other "special scenarios" (including reports of drug-drug/drug-food interaction, drug use during lactation or breast-feeding, lack of effectiveness, overdose, drug maladministration or accidental exposure, dispensing errors/medication errors, withdrawal or rebound symptoms, irrespective of whether a clinical event has occurred) and all SAEs will be collected into the patients case report form. The same will be done for any other information that may suggest a change in the benefit-risk profile for the drug.

Conditions that were already present at the time of informed consent should be recorded in the Medical History page of the patient's CRF. Adverse event monitoring should be continued for at least 30 days following the last dose of study treatment. Adverse events (including lab abnormalities that constitute AEs) should be described using a diagnosis whenever possible, rather than individual underlying signs and symptoms. When a clear diagnosis cannot be identified, each sign or symptom should be reported as a separate Adverse Event. AEs will not be collected beyond 30 days after the last dose of study treatment. The occurrence of adverse events should be sought by non-directive questioning of the patient (subject) during the screening process after signing informed consent and at each visit during the study. Adverse events also may be detected when they are volunteered by the patient (subject) during the screening process or between visits, or through physical examination, laboratory test, or other assessments. As far as possible, each adverse event should be evaluated to determine:

- The severity grade (CTCAE Grade 1-5)
- Its duration (Start and end dates)
- Its relationship to the study treatment (Reasonable possibility that AE is related: No, Yes)
- Action taken with respect to study treatment (none, dose adjusted, temporarily interrupted, permanently discontinued, unknown, not applicable).
- Whether medication or therapy was given (no concomitant medication/non-drug therapy, concomitant medication/non-drug therapy)
- Whether it is serious, where a serious adverse event (SAE) is defined as in Section 18.2 and which seriousness criteria have been met.
- Outcome (not recovered/not resolved, recovered/resolved, recovering/resolving, recovered/resolved with sequelae, fatal, unknown)

If the event worsens the event should be reported a second time in the CRF noting the start date when the event worsens in toxicity. For grade 3 and 4 adverse events only, if improvement to a lower grade is determined a new entry for this event should be reported in the CRF noting the start date when the event improved from having been Grade 3 or Grade 4.

All adverse events should be treated appropriately. If a concomitant medication or non-drug therapy is given, this action should be recorded on the Adverse Event CRF.

Once an adverse event is detected, it should be followed until its resolution or until it is judged to be permanent, and assessment should be made at each visit (or more frequently, if necessary) of any changes in severity, the suspected relationship to the study treatment, the interventions required to treat it, and the outcome.

18.2. Serious Adverse Events

18.2.1 Definitions

Serious adverse event (SAE) is defined as one of the following:

- Is fatal or life-threatening
- Results in persistent or significant disability/incapacity
- Constitutes a congenital anomaly/birth defect
- Is medically significant, i.e., defined as an event that jeopardizes the patient or may require medical or surgical intervention to prevent one of the outcomes listed above
- Requires inpatient hospitalization or prolongation of existing hospitalization
- Note that hospitalizations for the following reasons should not be reported as serious adverse events: Routine treatment or monitoring of the study indication
 - Progression/relapse of underlying disease (including fatal outcomes)
 - Elective or pre-planned treatment for a pre-existing condition that is unrelated to the indication under study and has not worsened since signing the informed consent
 - Social reasons and respite care in the absence of any deterioration in the patient's general condition
- Note that treatment on an emergency outpatient basis that does not result in hospital admission and involves an event not fulfilling any of the definitions of a SAE given above is not a serious adverse event.

18.2.2 Reporting

For patients who sign the Screening ICF, SAE collection will start upon signing the Screening ICF. SAEs will only be reported if the event is suspected to be causally related to a study procedure as assessed by the investigator (e.g. an invasive procedure such as biopsy). SAEs will be followed until resolution or until clinically relevant improvement or stabilization. If the Study ICF is not signed (screen failure), SAE collection ends 30 days after the last study related procedure.

For patients who sign the Study ICF, SAE collection starts at time of Study informed consent whether the patient is a screen failure or not.

To ensure patient safety, every SAE, regardless of suspected causality, occurring after the patient has provided Study informed consent and until at least 30 days after the patient has stopped study treatment must be reported to Safety Responsible within 24 hours of learning of its occurrence. Any additional information for the SAE including complications, progression of the initial SAE, and recurrent episodes must be reported as follow-up to the original episode within 24 hours of the investigator receiving the follow-up information. An SAE occurring at a different time interval or otherwise considered completely unrelated to a previously reported one should be reported separately as a new event.

Any SAEs experienced after the 30 day safety evaluation follow-up should only be reported to Safety Responsible if the investigator suspects a causal relationship to the study treatment.

Information about all SAEs is collected and recorded on the Serious Adverse Event Report Form; all applicable sections of the form must be completed in order to provide a clinically thorough report. The investigator must assess and record the relationship of each SAE to each specific study treatment (if there is more than one study treatment), complete the SAE Report Form in English, and submit the completed form within 24 hours to the Safety Responsible of the study. Detailed instructions regarding the SAE submission process and requirements for signatures are to be found in the investigator folder provided to each site.

Follow-up information is submitted in the same way as the original SAE Report. Each re- occurrence, complication, or progression of the original event should be reported as a follow-up to that event regardless of when it occurs. The follow-up information should describe whether the event has resolved or continues, if and how it was treated, whether the patient continued or withdrew from study participation.

If the SAE is not previously documented and is thought to be related to the study treatment, the Safety Responsible of the study and the Novartis safety desk may urgently require further information from the investigator for Health Authority reporting. Suspected Unexpected Serious Adverse Reactions (SUSARs) will be collected and reported to the competent authorities and relevant ethics committees in accordance with Directive 2001/20/EC or as per national regulatory requirements in participating countries.

All Collected SAEs in patients exposed to the Novartis drug and SUSARs should be transferred to Novartis safety desk within 15 calendar days of awareness.

The FISM-ETS Pharmacovigilance will provide Novartis with a copy of the development safety update report (DSUR) at the time of submission to the Regulatory Authority and Ethics Committees.

CONTACT DETAILS FOR PHARMACOVIGILANCE

[name]

☎: [name]

[contact]

e-mail: [contact]

